#### **8.3.2 Application Site Reactions**

At Visits 1, 2, 3 and 4 the Investigator will evaluate the subject for local application site reactions.

Signs and Symptoms recorded at each visit will be compared between treatment groups. Descriptive summaries (number of observations, mean, standard deviation, minimum, median and maximum) comparing the application site reactions for each treatment group will be presented by visit.

A frequency summary table comparing the application site reactions for each treatment group will be presented by visit.

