#### 8.5 Risks and Benefits

The risks and benefits to subjects enrolled in clinical research studies that include a Placebo treatment group must be carefully considered based on three main criteria, namely: the disease being treated, the availability, efficacy and safety of approved therapies, and the scientific and statistical requirements of the desired outcome of the research study. The Office of Human Rights Protection (OHRP), a Division of the United States Federal Government's Department of Health

A Multi-Center, Double-Blind, Randomized, Vehicle-Controlled, Parallel-Group Study Comparing Tazarotene Cream 0.05% to TAZORAC® (tazarotene) Cream 0.05% and Both Active Treatments to a Vehicle Control in the Treatment of Stable Plaque Psoriasis

and Human Services, has issued a detailed guidebook to IRBs that includes discussion on the use of placebos in clinical studies.

Randomized subjects will be enrolled in the study for  $85 \pm 4$  days. Although the potential for any drug-related side effects of significance occurring during the study is low, the risk is higher in the two active treatment groups than in the Placebo group. Topical application of Tazarotene can lead to drug-related effects, mainly affecting the application sites: skin itching, irritation, dryness and burning or pain sensation represent the most common side effects.

All subjects enrolled in this study will receive Investigator evaluation of their condition over 85 days. In addition, the subject will be paid for their participation, and any payments will be reviewed by the IRB and disclosed to the subject, via the informed consent form (ICF).

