## **10.6.10** Application Site Reactions

At Visit 1, the Investigator will grade the individual signs and symptoms per Appendix C. This will serve as a baseline for subsequent assessments of application site reactions. At Visits 2, 3 and 4, the Investigator will evaluate the subject for local application site reactions (erythema, dryness, burning/stinging, erosion, edema, pain, and itching) based on the scale provided in Appendix C. Reactions will be documented in source documents for each subject.

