## **11.8 Safety Analysis**

AEs will be classified using standard MedDRA terminology Version 18.1 or higher and summarized by treatment group. Summary tables comparing the type, date of onset, date of resolution, incidence, severity, relationship to the IP, outcome and action taken will be prepared by treatment group. Should sufficient data exist, AE frequencies will be compared among treatments using Fisher's exact test or a similar test.

Application site reactions (erythema, dryness, burning/stinging, erosion, edema, pain, itching) recorded at each visit will be compared among treatment groups. A descriptive analysis comparing the application site reactions for each treatment group will be created.

Concomitant medication use during the treatment period will be tabulated by subject.

Signs and symptoms of psoriasis will not be considered AEs, unless in the Investigator's opinion, they have increased in frequency and/or severity to such an extent that the Investigator/subject considers that it is in the subject's best interest to be dropped from continued participation in the study and given alternative therapy for their condition.

All randomized subjects who received IP will be included in the comparative safety analysis.

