#### 14.0 APPENDICES

#### 14.1 APPENDIX A: Investigator's Global Assessment of Disease Severity

Score	Grade	Definition	
0 None	No plaque elevation above normal skin level; may have residual non-		
	rione	erythematous discoloration; no psoriatic scale; no erythema	
1	Minimal	Essentially flat with possible trace elevation; faint erythema; no psoriatic scale	
2	Mild	Slight but definite elevation of plaque above normal skin level; may have up to moderate erythema (red coloration); fine scales with some lesions partially covered	
3	Moderate	Moderate elevation with rounded or sloped edges to plaque; moderate erythema (red coloration); somewhat coarse scales with most lesions partially covered	
4	Severe	Marked elevation with hard, sharp edges to plaque; severe erythema (very red coloration); coarse, thick scales with virtually all lesions covered and a rough surface	
5	Very Severe	· I ervinema (extreme red coloration), very coarse thick scales with all lesions	

To be eligible for participation in the study a subject must have a Baseline IGA score of 3, 4 or 5.

A subject shall be considered a "treatment success" if he/she has an IGA score of 0, 1 or 2 within the treatment area at the Week 12 visit.

A Multi-Center, Double-Blind, Randomized, Vehicle-Controlled, Parallel-Group Study Comparing Tazarotene Cream 0.05% to TAZORAC® (tazarotene) Cream 0.05% and Both Active Treatments to a Vehicle Control in the Treatment of Stable Plaque Psoriasis

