# 14.2 APPENDIX B: Psoriasis Area Severity Index at the Target Lesion Site

Score	Grade	Erythema	Scaling	Plaque Elevation
0	Clear	No evidence of erythema	No evidence of scaling	No evidence of plaques above normal skin level
1	Almost Clear	Pink discoloration, minimal erythema	Occasional fine scales hardly noticeable	Slight, just discernible elevation above normal skin level
2	Mild	Light red coloration	Slight but definite roughness, fine scale present, no cracking	Discernible elevation above normal skin level upon examination, but not pronounced
3	Moderate	Moderate redness, but not dark	Moderate roughness, somewhat coarse scaling	Definite plaque formation with rounded/sloped edges to plaque
4	Severe	Dark red coloration	Marked roughness, coarse/thick scaling, cracking may be evident	Marked elevation with hard, distinct edges to plaque
5	Very Severe	Very dark red coloration with induration present	Very thick scales covering extensive area, severe cracking/fissures may be evident	Very marked elevation, very hard and sharp edges to plaque

To be eligible for participation in the study a subject must have a minimum plaque elevation of at least moderate severity (score  $\geq$  3) at the target lesion site. The most severe lesion at Baseline should be identified as the target lesion.

A Multi-Center, Double-Blind, Randomized, Vehicle-Controlled, Parallel-Group Study Comparing Tazarotene Cream 0.05% to TAZORAC® (tazarotene) Cream 0.05% and Both Active Treatments to a Vehicle Control in the Treatment of Stable Plaque Psoriasis

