# T16.1.9.16 Summary of Application Site Reaction (Safety Population)

Signs and			Test	Reference	Placebo
Symptoms	Visit	Statistic	(N = xxx)	(N = xxx)	(N = xxx)
Erythema	1	n	XXX	XXX	XXX
		$Mean \pm SD$	$xx.x \pm xx.x$	$xx.x \pm xx.x$	$xx.x \pm xx.x$
		Median	XX.X	XX.X	XX.X
		Range	XX.X - XX.X	XX.X - XX.X	XX.X - XX.X
	2				
	3				
	4/ET				
Dryness					
Burning/Stinging					
Erosion					
Edema					
Pain					
Itching					
Test: Tazarotene Cream Reference: TAZORAC ® Placebo: Placebo (vehic	® (tazarotene) Cr	eam, 0.05% (Allergan,	Inc.)		
Path: L:\Studies_Sas_C	odes\Clinical Tr	ial \SAS\OU	T Created or	a: ddmmmyy hh:mm	Page 1 of

	Protocol /	0453-01-01/
T16.1.9.17 Summary of Frequency of Applicat (Safety Population)	ion Site Reaction	
T. (	Deferment	

Signs and			Test	Reference	Placebo
Symptoms	Visit	Statistic	(N = xxx)	(N = xxx)	(N = xxx)
Erythema	1	Absent	xxx (xx.x%)	xxx (xx.x%)	xxx (xx.x%)
		Mild	xxx (xx.x%)	xxx (xx.x%)	xxx (xx.x%)
		Moderate	xxx (xx.x%)	xxx (xx.x%)	xxx (xx.x%)
		Severe	xxx (xx.x%)	xxx (xx.x%)	xxx (xx.x%)
	2				
	3				
	4/ET				
Dryness					
Burning/Stinging					
Erosion					
Edema					
Pain					
Itching					
Reference: TAZORA	AC ® (tazarotene) Cre	Pharmaceuticals Inc.) eam, 0.05% (Allergan, Inc gera Pharmaceuticals Inc.)	.)		
th: L:\Studies_Sas_Co	odes\Clinical Trial\	\SAS\OUT	Created on: ddmmr	nyy hh:mm	Page 1 of N

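### Do the planned safety tables fail to count subjects whose application-site reactions worsened, or subjects by adverse-event severity, relationship and seriousness?

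*SAP*

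**What the plan says.** **Application-site reactions.** Protocol 10.6.10 has the Investigator grade the signs and symptoms of Appendix C at Visit 1 and adds: "This will serve as a baseline for subsequent assessments of application site reactions". Protocol 11.8 then commits to a comparison of the grades recorded at each visit and to a description by arm: "A descriptive analysis comparing the application site reactions for each treatment group will be created". SAP 8.3.2 repeats this ("Signs and Symptoms recorded at each visit will be compared between treatment groups") and specifies two outputs. One gives descriptive statistics by visit. The other is a frequency table: "A frequency summary table comparing the application site reactions for each treatment group will be presented by visit". The shells are T16.1.9.16 and T16.1.9.17, each with rows for Visits 1, 2, 3 and 4/ET.

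**Adverse events.** The opening line of SAP 8.3 bases every safety analysis on the Safety population. SAP 8.3.1 promises numbers and percentages of subjects with any AE, with discontinuation due to AEs, by severity, by relationship, and with serious AEs or death. Later paragraphs of 8.3.1 separately ask for counts of events by severity and by relationship. SAP section 9 describes the shells as a general layout whose headers, variable names and footnotes may be modified.

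**The concern.** Two things look wrong at first.

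First, Visit 1 is declared a baseline, yet no table compares a subject's later grade with it. By-visit summaries let improvement in some subjects offset worsening in others. They also do not show whether the same subjects or different ones are affected from visit to visit. The matter is not trivial, because Protocol 8.5 says that "skin itching, irritation, dryness and burning or pain sensation represent the most common side effects". Erythema is the hardest sign to read, since it is also a disease sign; the IGA grade for minimal disease, for example, is defined as "Essentially flat with possible trace elevation; faint erythema; no psoriatic scale".

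Second, the promised subject percentages by severity, relationship and seriousness have only one possible home, T16.1.9.10. There the rows come after a row giving the number of AEs reported. The shell states no unit, denominator or maximum-severity rule. Its group total is labelled as subjects randomized, although the table is for the Safety population. A programmer could print those rows per event.

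At stake is objective 3, the safety comparison of the three products.

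**Working it through.** **Step 1: promise against delivery.**

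| Promise | Shell | Delivered? |
|---|---|---|
| By-visit descriptive statistics for each sign (SAP 8.3.2) | T16.1.9.16 | Yes |
| By-visit grade frequencies (SAP 8.3.2) | T16.1.9.17 | Yes |
| Subjects with AEs by system organ class and term (SAP 8.3.1) | T16.1.9.11 | Yes, subject-based |
| Events by severity and by relationship (SAP 8.3.1) | T16.1.9.13, T16.1.9.14 | Yes, event denominators as asked |
| Subjects by severity, relationship, SAE and death (SAP 8.3.1) | T16.1.9.10 | Rows present; unit not stated in the shell |
| Count of subjects worse than their own Visit 1 grade | none | Not promised anywhere |

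T16.1.9.15 gives SAE event counts only. SAP 8.3.1 does not promise subject percentages by term for SAEs; the subject-level SAE item belongs in T16.1.9.10.

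**Step 2: what one visit's table leaves open.** The documents give no grade frequencies, so those below are assumed. Arm size is 855/3 = 285 at full enrolment. Take a sign graded absent or mild, present in n₁ subjects at Visit 1 and nₜ later, with all 285 seen at both visits. Let W be the number worse and I the number improved. Then

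- W − I = nₜ − n₁, which the tables do show;
- W lies between max(0, nₜ − n₁) and min(nₜ, 285 − n₁).

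If n₁ = 0, then W = nₜ and nothing is hidden. If n₁ = nₜ = 28, W is anywhere from 0 to 28 (28/285 = 9.8%). If n₁ = nₜ = 86, it is 0 to 86 (30.2%). With all four grades in use and 115/100/50/20 subjects at grades 0/1/2/3 at both visits, W runs from 0 to 285 − 115 = 170 (59.6%).

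**Step 3: across visits.** Let the sign be absent in everyone at Visit 1 and present in k subjects at each of Visits 2, 3 and 4. The number ever affected lies between k (the same subjects throughout) and 3k (no subject affected twice). For k = 14 the range is 14 to 42 (4.9% to 14.7%). For k = 28 it is 28 to 84 (9.8% to 29.5%).

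**Step 4: events against subjects.** If 10 of 100 events are severe, an event-based row prints 10.0% whether they came from 1 subject (1/285 = 0.4%), 5 subjects (1.8%) or 10 subjects (3.5%). Six SAEs in T16.1.9.15 could be 1 to 6 subjects (0.4% to 2.1%).

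**Step 5: does this spoil the comparison?** Randomisation makes the expected Visit 1 distribution the same in every arm. A between-arm difference in later frequencies therefore estimates a difference in W − I. Two arms can hide a difference in W only if a matching difference in I cancels it. The ranges in Steps 2 and 3 limit what a table can identify in the worst case; they are not expected errors.

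For T16.1.9.10, the text settles the unit. SAP 8.3.1 says subjects, SAP 8.3 says Safety population, and the shell is a layout subordinate to both. An event-based version would repeat the totals row of T16.1.9.13 and T16.1.9.14, so the mistake would be visible on the page. The label for randomized subjects should differ little from the Safety N, because Protocol 10.5.1 randomises and dispenses at the same visit.

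**The case for a change.** The best case for changing the plan is that a few subjects with lasting irritation and many with brief irritation can produce identical by-visit tables, as Step 3 shows. The AE tables are not a dependable substitute. Protocol 10.7 leaves it to the Investigator's opinion whether a changed site reaction becomes an AE, and Protocol 11.8 keeps psoriasis signs out of the AE data unless they worsen enough to warrant leaving the study for other therapy. Protocol 10.7.4 itself uses worsening after enrolment as the test for whether a pre-existing condition counts as an AE. A table of worst post-baseline grade against Visit 1 would need no new data.

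Most of this stands as a remark about informativeness: such a table would tell the reader something the planned ones do not. It does not show that the plan is wrong. Calling Visit 1 a baseline is not a commitment to a shift analysis, and both planned tables display Visit 1 beside the later visits. For erythema, where netting matters most, a worsening count would still not separate irritation from psoriasis. The analysis is descriptive and no decision rule depends on it, so the table can be produced from the collected grades if someone wants it.

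On adverse events, the criticism of the T16.1.9.10 layout is fair as far as it goes: the row order suggests events and the group total is loosely labelled. The criticism of the event-based tables is not, because SAP 8.3.1 asks for them.

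**Conclusion.** No change follows. The first part asks for an additional descriptive table that neither document promises; the planned randomised comparison by visit is sound without it. The second part is a clerical looseness in one shell, already resolved by SAP 8.3 and 8.3.1 together with the latitude in section 9. An analyst following the SAP text would count subjects over the Safety population.

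The size cannot be estimated from the documents. The ranges above rest on assumed frequencies and 285 per arm, and they describe only what the tables leave unidentified. The conclusion assumes that the SAP text governs where a shell is silent. It concerns safety reporting alone: the equivalence interval, the superiority tests and the sample size are unaffected.

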## 10.3.4 Withdrawal of Subjects from the Study

Subjects will be advised that they are free to withdraw from the study at any time. Additionally, the sponsor may cease the study at any time. If necessary, the Investigator may withdraw a subject from the study to protect the health of that subject. The clinical study report will include all reasons for early withdrawals.

Reasons for removal may include the following:

- Subject withdraws consent for any reason
- Subject's condition has worsened to the degree that the Investigator feels it is unsafe for the subject to continue in the study
- Lack of treatment effect

A Multi-Center, Double-Blind, Randomized, Vehicle-Controlled, Parallel-Group Study Comparing Tazarotene Cream 0.05% to TAZORAC® (tazarotene) Cream 0.05% and Both Active Treatments to a Vehicle Control in the Treatment of Stable Plaque Psoriasis

- Significant adverse event (AE) that could affect the safety of the subject or the validity of evaluation of the subject's clinical state to an extent considered significant by the Investigator
- Subject's IP becomes unblinded
- There is a protocol deviation that, in the Investigator's, Medical Monitor's or Sponsor's opinion, would compromise the safety of the subject or integrity of the data
- The subject is lost to follow-up. The Investigator will document efforts to attempt to reach the subject at least twice by telephone and by a certified follow-up letter before considering that the subject as lost to follow-up
- Pregnancy
- Administrative reasons
- Other (If the reason for withdrawal is not listed, 'Other' will be specified and the reason noted)

Subjects who withdraw or are removed from the study will not be replaced. The Investigator may refer the subject for appropriate care if the subject withdraws due to safety concerns, as applicable. All subjects who are randomized will be included in the safety monitoring tabulating all AEs experienced after dosing until withdrawal from the study.

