# **10.3.5 Early Termination**

If a subject terminates from the study early, all efforts will be made to complete Visit 4 study procedures, obtain any outstanding data and collect all IP. For early termination, the Investigator shall fully document the reason for early termination and the date of removal.

In the event that a subject discontinues from the study at any time due to an AE, the reason for discontinuation, the nature of the event and its clinical course must be fully documented. For such a subject, the Investigator should follow the subject until the AE has resolved, has become clinically insignificant, is stabilized, is confirmed to be ongoing at the end of the study, or the subject is lost to follow-up. Should a serious adverse event (SAE) be noted, procedures stated in section 10.7.4 must be followed. Should pregnancy be noted, procedures stated in section 10.7.6 must be followed.

Subjects who discontinue early because of lack of treatment effect after completing four weeks of treatment will be included in the per-protocol (PP) population as treatment failures provided they had no significant protocol deviations (PDs). Any PD that would compromise the integrity of the data will be considered significant.

Subjects who discontinue early due to worsening condition and require alternate or supplemental therapy for the treatment of their plaque psoriasis during the study should be discontinued, included in the PP population analysis as treatment failures (provided they had no significant PDs during their time of study participation), and referred for effective treatment outside of the study.

Subjects who discontinue early for reasons besides lack of treatment effect or worsening of condition should be excluded from the PP population, but included in the modified Intent-to-Treat

A Multi-Center, Double-Blind, Randomized, Vehicle-Controlled, Parallel-Group Study Comparing Tazarotene Cream 0.05% to TAZORAC® (tazarotene) Cream 0.05% and Both Active Treatments to a Vehicle Control in the Treatment of Stable Plaque Psoriasis

(mITT) population using the last observation carried forward (LOCF), provided they administered at least one dose of randomized IP and completed at least one post-dose evaluation.

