#### 10.5.4 Visit 4: (Day 85 ± 4 days) End of Study Visit or Early Termination

- 1. Assess Health Status: Review the subject's use of any new or ongoing concomitant medications and report any AEs.
- 2. **Pregnancy Test**: A urine pregnancy test will be required of all female subjects of childbearing potential.
- 3. Vital Signs: Blood pressure, pulse, temperature and respiration rate will be recorded for each subject.
- 4. **IGA**: A Medical Investigator will perform a severity rating according to the IGA to determine the severity of the plaque psoriasis in the treatment area. See Appendix A.
- 5. **PASI Assessment**: A Medical Investigator will perform the PASI Assessment of the target lesion site. See Appendix B.
A Multi-Center, Double-Blind, Randomized, Vehicle-Controlled, Parallel-Group Study Comparing Tazarotene Cream 0.05% to TAZORAC® (tazarotene) Cream 0.05% and Both Active Treatments to a Vehicle Control in the Treatment of Stable Plaque Psoriasis

- 6. **Application Site Reactions**: A Medical Investigator will evaluate any application site reactions (see Appendix C) since the last visit.
- 7. Collect and Review Subject's Diary: Collect the diary from the subject and review for compliance with the protocol requirements.
- 8. **IP Collection**: Collect all used and unused tubes and return them to their corresponding kit box(s) for storage. Record any lost or significantly damaged (i.e., punctured) IP.
- 9. Discharge from Study: Discharge the subject from the study.

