## 10.6.15 Subject Dosing Instructions and Diary

Subjects will be instructed to use the IP as described in section 10.4.1.

The site will instruct the subject on when the first dose of IP will be applied, which will be considered Day 1. The subject will record the date of Day 1 in their diary.

For all other subjects, the first dose (Day 1) of IP will be applied on the evening of Visit 1.

Subjects will be provided with a diary at Visits 1, 2 and 3. Subjects will be asked to record the date of Day 1, the time and date of each dose, any missed doses, any AEs that have occurred and any concomitant medications utilized throughout the study. The site will review the diary and evaluate the subject's compliance with the protocol at Visits 2, 3 and 4, based on any new additions to their medical history, new or changed concomitant medications, AEs and dosing compliance. If the diary is not returned, the staff will collect available information based on discussion with the subject. The subject will also be reminded of the medications and/or treatments that are prohibited during the study.

If the subject is no longer eligible for participation at Visit 2 and/or 3, the site will conduct Early Termination (Visit 4) procedures.

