## 12.3.4 Source Documents and Case Report Forms

All subjects will be identified by initials and date of birth. Randomized subjects will also have a unique subject randomization number. Source documents will be used to record all study-related data. Source document entries will be used to complete eCRFs which will record all critical study information. A set of eCRFs will be completed for each subject enrolled in the study. All data from eCRFs will be reviewed, evaluated and signed by the Investigator, as required. All eCRFs will be cross referenced to source documentation by the study monitor and/or the sponsor to ensure accurate transcription of the data.

The original source documents and a copy of the corresponding eCRFs (electronic or print out) will be retained by the Investigator. Subjects who terminate early from the study will have the Visit 4 (End of Study/Early Termination) Source/eCRF completed.

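### The by-visit tables of graded application-site reactions pool early-termination assessments from any study day with the Day 85 ± 4 assessments in one 4/ET row; print Early Termination as its own row

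*SAP*

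**What the plan says.** SAP 8.3.2 sets the assessment times: "At Visits 1, 2, 3 and 4 the Investigator will evaluate the subject for local application site reactions". It plans descriptive statistics and a frequency table for each reaction, and of the latter it says: "A frequency summary table comparing the application site reactions for each treatment group will be presented by visit". The section does not mention early termination.

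The shells do. T16.1.9.16 (means and medians) and T16.1.9.17 (frequencies by grade) have rows labelled 1, 2, 3 and 4/ET. The listing L16.2.7.2 and the vital-signs shell T16.1.9.18 use the same label.

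The protocol determines which records fall under that label:

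- Section 10.3.5, on any subject who stops early: "all efforts will be made to complete Visit 4 study procedures".
- Section 12.3.4: "Subjects who terminate early from the study will have the Visit 4 (End of Study/Early Termination) Source/eCRF completed".
- Section 10.6.15: "If the subject is no longer eligible for participation at Visit 2 and/or 3, the site will conduct Early Termination (Visit 4) procedures".
- Section 10.5.4, among the Visit 4 or Early Termination procedures: "A Medical Investigator will evaluate any application site reactions", covering the period since the last visit.

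**The concern.** A by-visit table is useful only if each row stands for a known time on treatment. Rows 2 and 3 do. The last row mixes subjects who completed about 12 weeks with subjects who may have stopped in the first weeks, and the table gives no means of separating them.

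The mixing is unlikely to be random with respect to what is measured. Protocol 8.5 says of tazarotene that "skin itching, irritation, dryness and burning or pain sensation represent the most common side effects", and Protocol 10.3.4 lists among the reasons for removal: "Significant adverse event (AE) that could affect the safety of the subject". Some early leavers may therefore be the subjects with the worst local reactions. Their last grades would raise the 4/ET row and be absent from the row for the time at which they occurred.

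Comparing the safety of the three products is the third study objective, and these two tables are the only planned summaries of the graded reactions. If the arms differ in how many subjects leave because of irritation, the 4/ET row can differ between arms even when subjects still on treatment at Week 12 have the same rates.

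**Working it through.** **Table structure.** The documents give no figure on this point, so there is nothing to reproduce. Set side by side, the passages give three steps:

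1. Early leavers are assessed under Visit 4 procedures on the day they leave (Protocol 10.3.5, 10.5.4, 10.6.15) and recorded on the Visit 4 form (12.3.4).
2. The shells summarise Visit 4 and ET as one row.
3. Neither document visibly assigns an early-termination record by study day or gives it a separate row.

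The pooling follows. For a subject stopped at Visit 2 or 3, the documents do not say whether that visit's own form is completed as well. A grade held only on the Visit 4 form goes to the 4/ET row.

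**Inputs for an illustration.** From the documents: up to 855 randomized 1:1:1, so 855/3 = 285 per arm. Assumed, because the documents give no such figures: 82% completers (0.82 × 285 = 233.7), a true Week 12 moderate or severe rate of 2%, 60% of irritation leavers graded moderate or severe, and 1%, 2% or 5% of an arm leaving for irritation.

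Row rate = (n_ET × g_ET + n_comp × g_12) / (n_ET + n_comp), with n_comp × g_12 = 233.7 × 0.02 = 4.674.

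| Leaving for irritation | n_ET | Calculation | 4/ET row |
|---|---|---|---|
| 1% | 2.85 | (1.71 + 4.674)/236.55 | 2.7% |
| 2% | 5.70 | (3.42 + 4.674)/239.40 | 3.4% |
| 5% | 14.25 | (8.55 + 4.674)/247.95 | 5.3% |

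The Visit 4 rate is 2.0% in each case.

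**Other leavers.** The table counts only irritation leavers. If all remaining non-completers also had an assessment, graded at the 2% rate, the 5% case becomes (8.55 + 270.75 × 0.02)/285 = 13.965/285 = 4.9%.

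**Direction.** If the 5% who leave have no moderate or severe reactions, the row falls to 4.674/247.95 = 1.9%. The pooling can dilute as well as inflate.

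**Between arms.** If 5% leave one active arm and 2% the other, and both have the same 2% rate at Week 12, the rows differ by 5.33% − 3.38% = 1.95 percentage points. With equal leaving and equal grades, they do not differ.

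**Visit 2 row.** This is a separate and deliberately strong assumption: all leavers stop at or before Visit 2, all are graded severe, about 2% of those who stay are severe, and there are no other losses. Counts are rounded to whole subjects. With 2% leaving, the Visit 2 row shows 6/279 = 2.2%, against 12/285 = 4.2% with the leavers included. With 5% leaving it shows 5/271 = 1.8%, against 19/285 = 6.7%.

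**The case against.** The strongest case on the other side is that this is a display detail with limited consequences. Most of its parts are right, and they set the limits of the point.

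- **The label discloses the pooling.** A reader might infer that early irritation is presented as Week 12 irritation. The documents do not support that. The row is headed 4/ET, and the protocol defines Visit 4 as End of Study or Early Termination. What remains is that the two components cannot be separated.
- **Irritation is not lost to the safety analysis.** A reader might infer that these tables are the only view of local tolerability by arm. They are not. Protocol 10.7 has the investigator judge whether a change in an application-site reaction is an adverse event. SAP 8.3.1 summarises AEs by arm, severity and relationship, along with discontinuations due to AEs, and L16.2.7.1 lists AE dates. These outputs depend on that judgement, however, and their summaries show neither the grades nor a time course.
- **Earlier grades stay in place.** A subject graded at Visit 2 who leaves later remains in the Visit 2 row. Only the early-termination assessment is displaced.
- **The size is assumed.** No rate of leaving for irritation is given, and Protocol 8.5 calls the potential for significant drug-related effects low. Visit 4 grades also cover the period since the last visit, so even completers' values are not purely Day 85 readings.
- **The shells may be changed.** SAP 9 describes them as a general layout. That makes the correction easy but supplies no rule. With the SAP text silent, the row label is the only instruction the programmer has.

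**Conclusion.** The point holds as a low-cost improvement to the graded tolerability tables. As planned, the 4/ET row pools assessments from any study day with those at Day 85 ± 4. It has no defined time point, and early-termination grades given at or before Visit 2 or 3 are absent from those rows.

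The size and direction in this trial cannot be stated. Under the assumed inputs, a 2.0% Week 12 rate would appear as 2.7% to 5.3% when 1% to 5% of an arm leaves for irritation. Leavers without irritation would pull the row down instead.

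A reader might go further and conclude that the plan hides a difference between Test and Reference. The documents do not support that: such a bias needs different leaving rates or grades in the two arms, and nothing in the plan indicates them. The tables are descriptive, and the equivalence and superiority analyses are unaffected.

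**What to change.** In SAP 8.3.2 and shells T16.1.9.16 and T16.1.9.17, print Early Termination as a separate row, and keep the Visit 4 row to assessments made in the Day 85 ± 4 window. State this in the text of 8.3.2 as well as in the shells. In T16.1.9.18, use only the separate row: vital signs are scheduled at Visits 1 and 4 alone, so assigning early-termination records to Visits 2 or 3 would create rows made up entirely of early leavers.

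Do not assign early-termination records to Visit 2 or 3 by the nearest scheduled day unless a rule for duplicates is also given. A subject seen on Day 28 who terminates on Day 38 would be nearest to Visit 2 (the midpoint between Days 28 and 56 is Day 42) and would then have two Visit 2 records.

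The separate row does not put leavers' grades back into the Visit 2 figure. It does show them by arm and gives the Visit 4 row a defined time. The visit dates needed are already listed in L16.2.5.1. The cost is a sentence in the SAP, a row split in the shells and a slightly longer table.
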